6.4. Duration of the recruitment period

The recruitment period is estimated to last at 10 months. Patients should use the cream throughout the treatment period.

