2.7. Expected duration of the study

The overall duration of the study is expected to be 12 months from the start of recruitment of the populations until the last follow-up control and analysis of the data generated.

The intervention (application of the cosmetic cream) will take place from the beginning to the end of the chemotherapy treatment, with 1 daily application of the product (PB-011 or PB-012) on the hands. If sensory discomfort or, in the worst case, peripheral neuropathy develops during the period of chemotherapy or immunocytostatic treatment, the application shall be increased to twice daily on the affected areas (usually hands and feet). In case of lack of efficacy of the product, the investigator in charge may withdraw the subject from the study after three months of application of the product.

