6. SELECTION OF SUBJECTS

The inclusion of 120 patients who have been diagnosed with cancer in stages I-III and who are going to start chemotherapy treatment is proposed. Once the treatment is finished, the degree of cutaneous comfort will be compared between the patients who have developed peripheral neuropathy in both groups.

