7.2. Study development

When a subject meets all the inclusion criteria and none of the exclusion criteria and has signed the informed consent document, he/she is electable to enter the study. The researchers will collect the data of each volunteer and notify Prospera Biotech of their inclusion. Patients will

receive the cream when they start the chemotherapy treatment. Creams will be either sent directly to the participants' home or sent in advance to the centers and stored there at room temperature (15-25°C) until distributed to participants. The principal investigator will create the Data Notebook for each subject, anonymizing the personal and clinical data in all cases. The type of product to be assigned will be determined by the randomization procedure.

Subjects taking part in the study should apply a sufficient amount of cream to their hands once a day for the duration of their chemotherapy treatment. Those subjects who develop skin sensitivity or peripheral neuropathy should undergo the following procedures:

1. Increase the frequency of use of the cream to twice a day in all affected areas.
2. Once the chemotherapy treatment is finished: evaluation of the degree of skin satisfaction by means of a questionnaire that assesses the Dermatology Life Quality Index [DLQI] (Annex II) and the degree of satisfaction with the cream (Annex IV). Evaluation of the discomfort generated by peripheral neuropathy through a follow-up questionnaire (Annex III). Measurement of skin sensitivity using Von Frey hairs for patients who voluntarily wish to do so. These procedures will be carried out by the study collaborators of each center. In case of need, Prospera Biotech team could also contribute to make the follow-up (questionnaires) telematically.

The study procedures are included in section 8.2.

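### Ten months of recruitment inside a 12-month study leaves at most two months for the last entrant's chemotherapy, final assessment and all analysis, so the stated duration does not fit an end-of-chemotherapy endpoint

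*Combined protocol and SAP*

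**What the plan says.** Two timeline figures matter.

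- **Total duration.** Section 2.7 expects "12 months from the start of recruitment of the populations until the last follow-up control and analysis of the data generated". Sections 1 and 3 also put the project at 12 months.
- **Recruitment.** Section 6.4: "The recruitment period is estimated to last at 10 months".

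The rest of the plan ties each patient's follow-up to that patient's own chemotherapy.

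- **Entry.** Under sections 6.1 and 6.3, patients have had at most one chemotherapy session when they join. Section 7.2 supplies the cream when chemotherapy starts.
- **Exposure.** Section 2.7: "The intervention (application of the cosmetic cream) will take place from the beginning to the end of the chemotherapy treatment". Section 7.2 has the cream applied "for the duration of their chemotherapy treatment".
- **Assessment.** Section 7.2: "Once the chemotherapy treatment is finished: evaluation of the degree of skin satisfaction by means of a questionnaire". Section 8.2 likewise schedules the DLQI, the discomfort questionnaire and the cream satisfaction questionnaire at the end of treatment, for patients who develop discomfort.
- **Comparison.** Section 6: "Once the treatment is finished, the degree of cutaneous comfort will be compared between the patients who have developed peripheral neuropathy in both groups".

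Section 2.7 also provides that, where the product lacks efficacy, "the investigator in charge may withdraw the subject from the study after three months of application of the product". No section gives a chemotherapy length, a minimum follow-up, a data cut-off date, or a rule for patients still on chemotherapy at month 12.

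**The concern.** The 12 months cannot be read as accrual time alone, because section 2.7 places both the last follow-up and the analysis inside them. Once recruitment has taken ten, the last entrant has two months or less for nearly a whole course of chemotherapy and the final questionnaires, and the analysis must fit into the same two months.

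The end-of-treatment comparison is at stake. If the calendar were enforced, the patients without a final assessment would be those who entered late or had longer regimens. Any cancer type is eligible (section 6.3), so regimen length may well vary, and the loss would then depend on it. If the calendar were not enforced, the duration stated in three sections would be wrong.

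**Working it through.** **Inputs from the documents**

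- Total duration T = 12 months, including last follow-up and analysis (section 2.7).
- Recruitment R = 10 months (section 6.4).
- Planned entrants N = 120, 60 per arm (section 6.3).
- Three-month withdrawal provision (section 2.7).

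**Assumptions, not in the documents**

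- D = months of chemotherapy remaining at entry.
- a = months kept for analysis at the end.
- Uniform accrual over the ten months.

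**Step 1. Time left for the last entrant.** T − R = 12 − 10 = 2 months, less a.

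**Step 2. Check against the plan's own three-month point.** A patient entering at month 10 reaches three months of application at 10 + 3 = month 13. The latest entry that reaches it by month 12 is 12 − 3 = month 9. Anyone entering after month 9 would get there only after the stated end of the study.

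**Step 3. Condition for the timeline to work.** A patient entering at month t finishes chemotherapy at t + D and must do so by 12 − a. For the last entrant (t = 10) this requires D ≤ 2 − a.

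**Step 4. Illustrative share still on chemotherapy at the close.** The latest entry that completes is month 12 − a − D, so

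share = max(0, [10 − (12 − a − D)] / 10) = max(0, (D + a − 2) / 10).

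| D (months) | a = 0: share (entrants of 120) | a = 1: share (entrants of 120) |
|---|---|---|
| 2 | 0% (0) | 10% (12) |
| 3 | 10% (12) | 20% (24) |
| 4 | 20% (24) | 30% (36) |
| 6 | 40% (48) | 50% (60) |

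For example, with D = 4 and a = 0: (4 + 0 − 2)/10 = 0.20, and 0.20 × 120 = 24.

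These are shares of all entrants. The final questionnaires go only to patients who develop discomfort or neuropathy, so the number of lost assessments would be smaller than the counts shown, by an amount the documents do not allow one to estimate.

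**Step 5. Duration the design implies.** R + D + a = 10 + D + a. For D = 3 this is 13 months plus analysis; for D = 6, 16 months plus analysis.

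**The case against.** The best reply is that both durations are forecasts: section 2.7 speaks of an expected length and section 6.4 of an estimate. The operative text in sections 6.4, 7.2 and 8.2 follows each patient to the end of that patient's own treatment. On that reading a missed forecast produces an overrun and no data are lost. This stands, and it limits the point. It does not remove it, because the stated duration would still be wrong and nothing in the plan says that follow-up continues past month 12.

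A reader might infer more than the documents support in four ways.

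- **That the endpoint is cut off for late entrants.** No section writes a cut-off. Truncation is one of two possible outcomes and depends on closing at month 12.
- **That section 2.7 expects at least three months of application for everyone.** The clause permits withdrawal for lack of efficacy. It shows that the plan contemplates some courses lasting that long, and sets no minimum or expected length.
- **That late entrants leave the modified intention-to-treat set.** Section 12 requires satisfaction data, without specifying an end-of-chemotherapy value. Section 3 mentions fortnightly questionnaires for patients with discomfort, which sections 7.2 and 8.2 do not schedule. If these are collected, some late entrants could stay in the set. They would still lack the end-of-treatment value that section 6 compares.
- **That power falls by a stated amount from 95%.** Such figures would start from 60 analysed per arm, but section 6 compares only patients who develop neuropathy, so the analysed number is uncertain whatever the calendar. The 2-point difference and SD of 3 in section 6.3 are also given for a 0 to 10 satisfaction scale (or, as an alternative, a 2-point Von Frey difference), while the main variable in section 8.1 is the DLQI.

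It is also true that if remaining courses lasted two months or less, with no analysis time reserved, nobody would be missed. The documents do not say that they do. No bias between arms is claimed.

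**Conclusion.** The stated duration is wrong as written. Sections 2.7 and 6.4 leave at most two months after the last entry, and that cannot be reconciled with an end-of-chemotherapy assessment unless remaining courses are no longer than two months less analysis time. The two-month figure and the month-9 boundary follow directly from the documents' own numbers.

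The consequence is conditional: either an overrun, or, if the study closes at month 12, missing end-of-chemotherapy assessments for late entrants and longer regimens. With no time kept for analysis, the share of entrants affected runs from 0% at D = 2 to 40% at D = 6. That range rests on uniform accrual and an assumed course length and is only an illustration. The correction should be made, since it is cheap and protects the end-of-treatment comparison.

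**What to change.** In sections 1, 2.7 and 3:

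1. Define the end of the study as the end-of-chemotherapy assessment of the last randomised patient.
2. State the longest expected chemotherapy course among eligible patients, and restate the total duration as ten months of recruitment plus that course plus analysis time.
3. State that no patient's follow-up is closed at month 12.

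The cost is a text change in three sections and a calendar longer by some months, with no extra patients. On the assumed courses of 3 to 6 months, the total would be about 13 to 16 months plus analysis.

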7. PRODUCT DESCRIPTION

7.1. Product

Subjects who meet the inclusion/exclusion criteria and who become part of the study may take any medication that their physician deems appropriate, excluding those specified in the exclusion criteria.

Patients participating in the study will apply:

Cosmetic creams Ref. PB-011 and PB-012.

Tradename: Nocisens.

Business owner: Prospera Biotech S.L.

Composition:

- PB-011: Capric Triglyceride, Glyceryl Behenate, Glyceryl Stearate, Hydrogenated Castor Oil, Diethylene Glycol Monoethyl Ether, Tocopherol, Hydroxymethoxyiodobenzyl Glycolamide Perlargonate.
- PB-012: Capric Triglyceride, Glyceryl Behenate, Glyceryl Stearate, Hydrogenated Castor Oil, Diethylene Glycol Monoethyl Ether, Tocopherol.

7.2. Study development

When a subject meets all the inclusion criteria and none of the exclusion criteria and has signed the informed consent document, he/she is electable to enter the study. The researchers will collect the data of each volunteer and notify Prospera Biotech of their inclusion. Patients will

receive the cream when they start the chemotherapy treatment. Creams will be either sent directly to the participants' home or sent in advance to the centers and stored there at room temperature (15-25°C) until distributed to participants. The principal investigator will create the Data Notebook for each subject, anonymizing the personal and clinical data in all cases. The type of product to be assigned will be determined by the randomization procedure.

Subjects taking part in the study should apply a sufficient amount of cream to their hands once a day for the duration of their chemotherapy treatment. Those subjects who develop skin sensitivity or peripheral neuropathy should undergo the following procedures:

1. Increase the frequency of use of the cream to twice a day in all affected areas.
2. Once the chemotherapy treatment is finished: evaluation of the degree of skin satisfaction by means of a questionnaire that assesses the Dermatology Life Quality Index [DLQI] (Annex II) and the degree of satisfaction with the cream (Annex IV). Evaluation of the discomfort generated by peripheral neuropathy through a follow-up questionnaire (Annex III). Measurement of skin sensitivity using Von Frey hairs for patients who voluntarily wish to do so. These procedures will be carried out by the study collaborators of each center. In case of need, Prospera Biotech team could also contribute to make the follow-up (questionnaires) telematically.

The study procedures are included in section 8.2.

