6.1. Inclusion criteria

Patients must meet all the criteria that appear in this section to be included in the study.

- To be older than 18 years old.
- To be able to complete questionnaires.
- Give informed consent in writing.
- Being able to apply the product under test by oneself.
- To have been diagnosed with stage I-III primary cancer.
- To have received a maximum of one treatment session with chemotherapy (derivatives of taxane, platinum or vincristines).
- Eastern Cooperative Oncology Group (ECOG) performance status (PS) 0-2.
- Life expectancy greater than or equal to 6 months.

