6.3. Expected number of subjects and justification

A total of 120 volunteers diagnosed with any type of cancer, in stages I-III, who are about to start or have received a maximum of 1 dose of chemotherapy treatment will be studied.

Two study populations are contemplated: (i) population that will receive the PB-011 cream; (ii) population that will receive the PB-012 cream. Both populations will apply the cream on their hands once a day. If sensory discomfort or, in the worst case, peripheral neuropathy appear during the chemotherapy treatment period, the application will be increased to twice daily on the affected areas (generally hands and feet).

The number of volunteers for the study is 60 for each population. This value is based on: (i) a difference of 2 points between both populations (PB-011 and PB-012), on a satisfaction scale of

0 to 10 points, with 0 being very dissatisfied and 10 very satisfied, or 2 points on the Von Frey scale; (ii) a variability (standard deviation) of 3 points in each population; (iii) a p-value of statistical significance <0.05 and, (iv) a probability of finding a statistically significant difference for the p-value <0.05 of 95%.

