12. STATISTICAL ANALYSES

The analysis of the results of this study will be approached from two perspectives. On the one hand, the modified intention-to-treat (MITT) population will be analyzed, which corresponds to all those subjects who have used the product at least once and for whom satisfaction data is available. On the other hand, a per-protocol analysis will be carried out in which all randomized subjects who have followed the study instructions until the end of the study will be included.

The clinical evaluation data may be analyzed as quantitative or qualitative variables. In the first case, the results will be expressed as mean \pm standard deviation, minimum and maximum. In the case of qualitative variables, the results will be expressed as frequency and percentage. For all the parameters to be measured (both clinical variables and responses to questionnaires) there will be a baseline measurement taken before the start of the protocol that will serve as a control measurement. The change in the main variable (degree of satisfaction) will be analyzed

using the paired Student's T test. The change in the secondary variables will be studied according to their nature (qualitative or quantitative variables) and applying the corresponding test in each case: Chi square, Student's T, ANOVA, Kruskal-Wallis or Mann-Whitney U. The impact of each variable on the main variable will be assessed, especially the impact of treatment, diagnosis, age and gender.

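### Cream is to start with chemotherapy, yet patients with one session already given are eligible, so baseline precedes first exposure in some patients and follows it in others

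*Combined protocol and SAP*

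**What the plan says.** Two sections fix the start of the cream. Section 2.7 says application "will take place from the beginning to the end of the chemotherapy treatment". Section 7.2 says patients will "receive the cream when they start the chemotherapy treatment". Sections 1, 3 and 6 describe the population in the same spirit, as patients who have yet to begin chemotherapy.

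The eligibility text is wider. Section 6.1 requires patients "To have received a maximum of one treatment session with chemotherapy", naming taxane, platinum and vincristine derivatives. Section 6.3 lists both kinds of patient, those "who are about to start or have received a maximum of 1 dose of chemotherapy treatment will be studied".

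For the analysis, section 12 promises, for every parameter, a "baseline measurement taken before the start of the protocol that will serve as a control measurement". Section 8.2 likewise places the first Von Frey measurement before the study starts. Neither ties baseline to the first chemotherapy session. Section 12 analyses change in the main variable with a paired t test. It also says the impact of each variable on the main one will be assessed, and singles out treatment, diagnosis, age and gender. Section 5.2 specifies simple randomisation.

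**The concern.** A patient enrolled after one session cannot start the cream at the beginning of chemotherapy. No section gives such patients a separate rule for cream start or for baseline.

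This carries into the analysis. For a chemotherapy-naive patient, the control measurement is free of exposure. For a patient with one session behind them, it follows exposure to the agents whose skin and sensory effects are being studied. Section 6.2 excludes only pre-existing neuropathy unrelated to chemotherapy, so early symptoms from a first session are not clearly screened out. Any first-session effect is counted as change in one group and absorbed into baseline in the other, and the paired test in section 12 pools the two. Nothing in section 12 separates them, and allocation is not stratified by prior session.

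**Working it through.** **1. The plan's own figure.** Section 6.3 gives a difference of 2 points, an SD of 3, significance at 0.05 (two-sided assumed) and 95% power. The two-sample t calculation gives n = 59.45, so 60 per arm, as stated. Power at 60 per arm is 95.2%.

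**2. The sections side by side.**

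| Section | Implication for a patient with one prior session |
|---|---|
| 2.7 and 7.2: cream starts with chemotherapy | Cannot be met |
| 1, 3 and 6: chemotherapy not yet begun | Not described |
| 6.1 and 6.3: up to one session or dose allowed | Eligible |
| 8.2 and 12: baseline before study or protocol start | Baseline follows first exposure |

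No other section resolves this.

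**3. Within-arm change.** Let a share f of patients be pre-treated, and let the first session shift their baseline by d points. Mean within-arm change then moves by f × d. Neither value is in the documents, so both are assumed:
- f = 10%, d = 0.5: 0.10 × 0.5 = 0.05 points
- f = 30%, d = 1: 0.30 × 1 = 0.3 points
- f = 50%, d = 2: 0.50 × 2 = 1.0 point

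**4. Chance imbalance between creams.** Take 60 analysed per arm, with the number pre-treated in each arm an independent Binomial(60, f). An imbalance of 10 percentage points or more is then a difference of at least 0.10 × 60 = 6 patients. The exact probabilities are:
- f = 10%: 9%
- f = 30%: 27%
- f = 50%: 32%

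Sections 7.2 and 8.2 give the end-of-treatment questionnaires to patients who develop discomfort, and section 6 compares those who develop neuropathy, so fewer than 60 per arm may be analysed. If 30 per arm are (assumed), the 27% at f = 30% becomes 48%.

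**5. What an imbalance does to the contrast.** It moves the difference between creams by the imbalance times the shift. At 10 percentage points and a 2-point shift that is 0.10 × 2 = 0.2 points, a tenth of the 2-point target.

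**6. Precision.** Assume the SD of 3 applies to change scores and includes the mix of patients. Prior session then explains R² = f(1 − f)d² / 9 of the variance, and the adjusted SD is 3 × √(1 − R²). At f = 30%, with 60 per arm and a 2-point difference:

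| Shift d | R² | Adjusted SD | Power (unadjusted 95.2%) |
|---|---|---|---|
| 0.5 | 0.21 × 0.25 / 9 = 0.6% | 2.99 | 95.3% |
| 1 | 0.21 × 1 / 9 = 2.3% | 2.96 | 95.6% |
| 2 | 0.21 × 4 / 9 = 9.3% | 2.86 | 96.7% |

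**The case against.** The case for treating this as wording only is a fair one.

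- **Randomisation.** A reader might infer that the comparison of creams is biased. The documents do not support that: simple randomisation balances prior session in expectation, and the test's error rate already allows for chance imbalance. This stands.
- **Small gain.** The largest power gain needs one session to shift the score by 2 points, as much as the whole difference sought between creams. Nothing in the documents says that one session shifts any score. At 0.5 to 1 point the gain is 0.1 to 0.4 percentage points. This stands, so power is not the main reason to act.
- **The SD.** Section 6.3 gives the SD of 3 for a 0 to 10 satisfaction scale or Von Frey points. It is not stated for change in the DLQI, the main variable in section 8.1. The power figures are illustrations.
- **No model to adjust.** A paired t test takes no covariate, so the fix must name the between-cream model. Section 12's list of factors is also open-ended, so an adjustment for prior session is not ruled out, but it is not prespecified either.
- **Dates and delivery.** A reader might infer that first-application dates are recorded only on the Annex V reaction form. That cannot be claimed, because the Data Notebook (Annex I) is not supplied. Nor does home delivery establish a further delay, since section 7.2 also allows cream to be sent to centres in advance.

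None of this removes the contradiction over cream start or the two meanings of baseline. Randomisation does not repair a within-arm change score.

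**Conclusion.** The inconsistency is real and lies in operative text. For pre-treated patients the stated cream start cannot be met and baseline follows first exposure, so within-arm change from baseline mixes two quantities. Under the assumed ranges, the mean within-arm change moves by 0.05 to 1.0 point. It would be tempting to say that change is understated. That holds only if the first session worsens scores, which the documents do not show.

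For PB-011 versus PB-012 the consequence is chance imbalance and a small precision loss, not systematic bias. The imbalance figures rest on assumed pre-treated shares and 60 analysed per arm, and rise if only patients with discomfort are analysed. The issue should be corrected because it makes the change score ambiguous and costs little to settle. It does not undermine the randomised comparison.

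**What to change.** 1. Reconcile sections 2.7, 6, 6.1, 6.3 and 7.2 on when the cream starts relative to the first chemotherapy session. Which rule applies is for the sponsor and investigators, and none is proposed here.
2. State in sections 8.2 and 12 when baseline is taken relative to that session.
3. In section 12, specify the between-cream comparison of change as a linear model (ANCOVA) with treatment, baseline value and prior session (0 or 1, known at the eligibility check) as prespecified terms. Present within-arm change by prior-session status.
4. Confirm that the Data Notebook records the dates of first application and first chemotherapy session for every patient, or add them.

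The cost is protocol wording, one extra model term and a little more analysis work, plus two date fields if they are not already there. No further patients or procedures are needed.

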8. STUDY DEVELOPMENT AND EVALUATION OF THE RESPONSE

8.1. Study variables

Main Variable: degree of skin satisfaction/comfort with the skin in the palmar and plantar regions, evaluated by means of the DLQI questionnaire.

Secondary Variables:

- Skin sensitivity quantifiable by the Von Frey filament test for patients who voluntarily so wish.
- Follow-up of discomfort skin sensations experienced by patients, evaluated by means of a brief questionnaire.

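### Section 6.3 offers a Von Frey difference as a basis for 60 per arm at 95% power, but the test is optional and 7.2 lists it only for symptomatic patients, so that power needs nearly everyone to be tested

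*Combined protocol and SAP*

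**What the plan says.** **Sample size (6.3).** "The number of volunteers for the study is 60 for each population". The stated basis is "a difference of 2 points between both populations (PB-011 and PB-012), on a satisfaction scale of" 0 to 10, "or 2 points on the Von Frey scale", with "a variability (standard deviation) of 3 points in each population", "a p-value of statistical significance <0.05" and a 95% chance of a significant result. No allowance is made for patients who are not measured.

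**Status of the test (8.1).** Von Frey is a secondary variable: "Skin sensitivity quantifiable by the Von Frey filament test for patients who voluntarily so wish". The main variable is the DLQI. Section 8.2 repeats that the test is voluntary.

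**Timing and population.** Three sections bear on this:
- Section 7.2 gives steps for subjects who develop skin sensitivity or neuropathy. Under the step that follows the end of chemotherapy it lists "Measurement of skin sensitivity using Von Frey hairs for patients who voluntarily wish to do so". It then refers to 8.2 for the study procedures.
- Section 8.2 has the threshold measured twice, before the study starts and after chemotherapy. It describes those measured as patients with post-chemotherapy polyneuropathy.
- Section 12 calls for a baseline on every parameter, clinical variables included. It defines the modified intention-to-treat set by available satisfaction data and gives no rule for missing Von Frey results.

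No section says when a patient decides whether to take the test, or whether that decision is binding.

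**The concern.** The sample-size statement treats Von Frey as if it were measured in the full randomised arm. Two filters stand between enrolment and a Von Frey result: the patient must volunteer and, under 7.2, must have developed symptoms. Either one takes the number tested below 60, and 6.3 allows for neither.

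There is also a question of who is tested. Section 8.2 defines the result as the lowest pressure that triggers pain. If patients may opt in or decline after months on the assigned cream, those with sore hands or feet could be less willing, and if the creams differ, the willing group could differ by cream. The comparison would then no longer be between the groups as randomised. Von Frey is the only variable in 8.1 that is not a questionnaire, so its result is likely to be read as the objective support for whichever cream is preferred.

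**Working it through.** **Inputs, all from 6.3:** difference 2, SD 3, significance level 0.05, power 95%, 60 per arm. Sidedness is not stated. Two-sided is assumed because it reproduces 60, whereas one-sided gives 49 by the normal formula.

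**Reproducing the plan's figure.**
- Normal approximation: n = 2(z₀.₉₇₅ + z₀.₉₅)² × SD²/δ² = 2 × (1.960 + 1.645)² × 9/4 = 58.5, so 59 per arm.
- Two-sample t test with standardised difference 2/3: n = 59.5, so 60 per arm, with power 95.2% at 60.

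The plan's 60 reproduces, and it has no slack.

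**Power at the number actually tested.** Number tested per arm = 60 × proportion eligible × proportion volunteering. Power is for the two-sided two-sample t test. The normal formula Φ(δ/(SD√(2/n)) − 1.96) gives values up to about 2.5 percentage points higher. The 80% symptomatic figure is borrowed from the Introduction, which gives it as an upper bound for neuropathy with taxanes. The volunteering rates are assumptions.

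| Scenario | Tested per arm | Power |
|---|---|---|
| Everyone tested | 60 | 95.2% |
| 80% symptomatic, all volunteer | 48 | 89.8% |
| All eligible, 75% volunteer | 45 | 87.9% |
| 80% symptomatic, 75% volunteer | 36 | 79.7% |
| All eligible, 50% volunteer | 30 | 71.9% |
| 80% symptomatic, 50% volunteer | 24 | 61.8% |
| All eligible, 25% volunteer | 15 | 42.2% |

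These figures accept SD 3 for Von Frey. Section 6.3 gives a single SD and does not define a Von Frey point, while 8.2 expresses the threshold in pressure units.

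**Dilution, as an illustration only.** Suppose a higher threshold is better, the true difference is 2 with SD 3, and the odds of taking the end test rise with the patient's own end-of-treatment threshold. Uptake is set at the stated rate for a patient midway between the two arm means.

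| Odds ratio for uptake per SD of threshold | Observed difference, 50% uptake | Observed difference, 80% uptake |
|---|---|---|
| 1 (unrelated) | 2.0 | 2.0 |
| 2.7 | about 1.7 | about 1.75 |
| 7.4 | about 1.3 | about 1.4 |

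If the creams do not truly differ, the same model gives a difference of zero at every odds ratio. It shrinks a real effect and does not create a false one. Nothing in the documents fixes the uptake or the odds ratio.

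**The case against.** A reader might infer that 7.2 puts the patient's choice after chemotherapy, so that volunteers select themselves by how their skin feels. The documents do not support that. Section 7.2 fixes when the measurement is made, not when the patient agrees to it. Section 8.2 has a pre-study measurement and section 12 requires a baseline. A patient who contributes a change from baseline would have volunteered before using the cream, and only refusal of the second test would then remain. This stands: selection by symptoms is a risk, not an established fact, and the dilution figures above rest on assumed inputs.

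It does not remove the risk. No section limits the final comparison to baseline volunteers, and the end test stays optional. Section 8.2 also does not clearly define a baseline cohort, because patients with post-chemotherapy polyneuropathy cannot be identified before chemotherapy.

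It is equally tempting to say that the trial cannot supply 60 per arm for Von Frey. That depends on uptake, which is not given. With 80% symptomatic and everyone willing, power is still about 90%.

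Finally, Von Frey is an optional secondary variable in a study whose summary calls it a pilot, and making a pain-threshold test voluntary is a reasonable choice. That limits the consequence. It does not justify naming the test in 6.3 as a basis for 60 per arm at 95% power.

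**Conclusion.** The point holds as a sample-size and consistency problem. The 95% in 6.3 applies to Von Frey only if essentially every enrolled patient is tested, and 7.2, 8.1 and 8.2 give no reason to expect that. Power is about 90% under a mild shortfall (48 per arm) and 62% to 72% if half volunteer (24 to 30 per arm). This assumes a two-sided test, SD 3 on the Von Frey scale and equal loss in both arms.

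Separately, 7.2 conflicts with 8.2 and section 12 on when and in whom the test is done, and the time of the patient's choice is left open. If uptake can depend on symptoms after the cream has been used, a real difference may be diluted by an amount the documents do not allow one to fix. If uptake is unrelated to pain there is no bias. The DLQI main comparison is not affected by this point.

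**What to change.** 1. In 6.3, delete "or 2 points on the Von Frey scale", or restate the Von Frey power at the expected number tested, with the assumed uptake and symptomatic proportion given and the Von Frey unit and SD defined.
2. Reconcile 7.2 with 8.2 and section 12, so that one statement says when the test is done and in whom. A tick box at consent does not by itself remove the restriction to symptomatic patients in 7.2, so this needs its own decision.
3. Ask for the Von Frey choice at informed consent, before a cream is assigned, and record yes or no in the Data Notebook. Take the baseline measurement that 8.2 already states.
4. In section 12, compare creams among patients who opted in at entry, and report by cream how many of them later decline the end test.

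The cost is one tick box and wording in 6.3, 7.2, 8.2 and 12. The test stays voluntary. The downsides are that patients cannot join the test late and that any Von Frey power still quoted will be less favourable than 95%.
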